8.5.4. Lost to Follow-Up

If attempts to contact the patient by telephone are unsuccessful, additional attempts should be made to obtain protocol-required follow-up information. It may be possible to obtain the information from other contacts, such as referring physicians or relatives. Attempts of contact should be documented in the patient's source documents. If a patient cannot be contacted despite all attempts, the patient will be considered lost to follow-up, and death information should be obtained through a public record search if local agencies permit.

8.6. End of Study for Individual Patients

Patients who end participation in the study do not contribute additional data at any subsequent visits (including the EOT and all follow-up visits). Patients who end participation in the study may do so under the following circumstances:

- Patient withdrew consent for study participation
 - Patients may voluntarily withdraw consent from the study at any time.
- Lost to follow-up
- Death
- Study termination by sponsor
- Other, as per the discretion of the sponsor or health authority

The reason for discontinuation from study participation will be recorded on the eCRF.

8.7. End of Study

The end of study is defined as the timepoint when the final data point is collected from the last patient in the study. This is when the last patient dies, withdraws consent, or is lost to follow up. Alternatively, the end of study is when the sponsor decides to terminate the study.

The sponsor has the right to terminate this study at any time. Reasons for terminating the study early include but are not limited to the following:

- The incidence or severity of AEs in this or other studies indicates a potential health hazard to patients
- Overall patient enrollment is unsatisfactory

The sponsor will notify each investigator if a decision is made to terminate the study. Should this be necessary, prematurely discontinued patients must be seen for an EOT Visit and Safety Follow-up Visit as described in Section 8.4 and Section 8.5.1.

The investigators may be informed of additional procedures to be followed to ensure that adequate consideration is given to the protection of the patients' interests. The investigator will be responsible for informing IRBs/IECs of the early termination of the study.

9. DATA HANDLING AND QUALITY ASSURANCE

This study will be organized, performed, and reported in compliance with the protocol, standard operating procedures (SOPs), working practice documents, and applicable regulations and guidelines. Site audits may be made periodically by the sponsor's or the contract research organization's (CRO's) qualified compliance auditing team, which is an independent function from the study team responsible for conduct of the study.

9.1. Data Collection

Data required by the protocol will be entered into the eCRFs in an electronic data capture (EDC) system that is compliant with all regulatory requirements or transmitted to BeiGene by third party vendors, as applicable.

Data collection in the eCRF must follow the instructions described in the eCRF Completion Guidelines (eCCGs). The investigator has ultimate responsibility for the collection and reporting of all clinical data entered in the eCRF. The investigator or designee as identified on Form FDA 1572 must sign the completed casebooks to attest to its accuracy, authenticity, and completeness.

Data contained in the eCRFs are the sole property of BeiGene and should not be made available in any form to third parties without written permission from BeiGene, except for authorized representatives of BeiGene or appropriate regulatory authorities.

9.2. Data Management/Coding

All final patient data, both eCRF and external data (e.g., laboratory data), collected according to the protocol, will be stored at BeiGene at the end of the study.

Standard procedures (including following data review guidelines, computerized validation to produce queries, and maintenance of an audit file which includes all database modifications) will be followed to support accurate data collection. Data will be reviewed for outliers, logic, data inconsistencies, and completeness.

During the course of the study, a study monitor will make site visits to review protocol compliance, compare eCRFs against individual patient's medical records, and ensure that the study is being conducted according to pertinent regulatory requirements.

eCRF entries will be verified with source documentation. The review of medical records will be performed in a manner to ensure that patient confidentiality is maintained. Checking the eCRFs for completeness, clarity, and cross checking with source documents is required to monitor the progress of the study. Direct access to source data is also required for inspections and audits and will be carried out giving due consideration to data protection and medical confidentiality.

Adverse events will be coded using the Medical Dictionary for Regulatory Activities (MedDRA[®]). Concomitant medications will be coded using the World Health Organization Drug Dictionary (WHO-DD). Concomitant diseases/medical history will be coded using the MedDRA[®].

9.3. Quality Assurance

To ensure compliance with GCP and all applicable regulatory requirements, the sponsor may conduct quality assurance audits. Regulatory agencies may also conduct a regulatory inspection of this study. Such audits/inspections can occur at any time during or after completion of the study. If an audit or inspection occurs, the investigator and institution agree to allow the auditor/inspector direct access to all relevant documents and to allocate his/her time and the time of his/her personnel to the auditor/inspector to discuss findings and any relevant issues.

10. SAFETY MONITORING AND REPORTING

The investigator is responsible for the monitoring and documentation of events that meet the criteria and definition of an AE or SAE as provided in this protocol.

10.1. Adverse Events

10.1.1. Definition and Reporting of an Adverse Event

An AE is defined as any unfavorable and unintended sign (including an abnormal laboratory finding), symptom, or disease (new or exacerbated) temporally associated with the use of a study drug, whether considered related to study drug or not.

Examples of an AE include:

- Worsening of a chronic or intermittent pre-existing condition including an increase in severity, frequency, duration, and/or has an association with a significantly worse outcome
- New conditions detected or diagnosed after study drug administration even though it may have been present before the start of the study
- Signs, symptoms, or the clinical sequelae of a suspected interaction
- Signs, symptoms, or the clinical sequelae of a suspected overdose of either study drug or a concurrent medication (overdose per se should not be reported as an AE or SAE)

When an AE or SAE occurs, it is the responsibility of the investigator to review all documentation (e.g., hospital progress notes, laboratory results, and diagnostics reports) relative to the AE or SAE. The investigator will then record all relevant information regarding an AE or SAE in the eCRF. However, there may be instances when copies of medical records for certain cases are requested by the sponsor. In this instance, all patient identifiers will be blinded on the copies of the medical records prior to submission to the sponsor.

10.1.1.1. Assessment of Severity

The investigator will make an assessment of severity for each AE and SAE reported during the study. AEs and SAEs should be assessed and graded based upon the NCI CTCAE v4.03.

Toxicities that are not specified in the NCI CTCAE will be defined as follows:

- Grade 1: Mild; asymptomatic or mild symptoms, clinical or diagnostic observations only, intervention not indicated
- Grade 2: Moderate; minimal, local, or noninvasive intervention indicated, limiting age-appropriate instrumental activities of daily living (ADL)
- Grade 3: Severe or medically significant but not immediately life-threatening; hospitalization or prolongation of hospitalization indicated, disabling, limiting self-care ADL
- Grade 4: Life-threatening consequences; urgent intervention indicated
- Grade 5: Death related to AE

Note: The terms “severe” and “serious” are not synonymous. Severity is a measure of intensity (for example, grade of a specific AE, mild [Grade 1], moderate [Grade 2], severe [Grade 3], or life-threatening [Grade 4]), whereas seriousness is classified by the criteria based on the regulatory definitions. Seriousness serves as the guide for defining regulatory reporting obligations from the sponsor to applicable regulatory authorities as described in Section 10.2.

10.1.1.2. Assessment of Causality

The investigator is obligated to assess the relationship between the study drugs and the occurrence of each AE or SAE. The investigator will use clinical judgment to determine the relationship. Alternative causes, such as natural history of the underlying diseases, concomitant therapy, other risk factors, and the temporal relationship of the AE or SAE to the study drug will be considered and investigated. The investigator will also consult the Pamiparib Investigator’s Brochure [59] and/or Product Information, for marketed products, in the determination of his/her assessment.

There may be situations when an SAE has occurred, and the investigator has minimal information to include in the initial report to the sponsor. However, it is very important that the investigator always makes assessment of causality for every SAE prior to transmission of the SAE report/eCRF to the sponsor since the causality assessment is one of the criteria used when determining regulatory reporting requirements. The investigator may change his/her opinion of causality in light of follow-up information, amending the SAE report/eCRF accordingly.

The causality of each AE should be assessed and classified by the investigator as “related” or “not related”. An AE is considered related if there is “a reasonable possibility” that the AE may have been caused by the study drug (i.e., there are facts, evidence, or arguments to suggest possible causation). A number of factors should be considered in making this assessment, including:

- Temporal relationship of the AE to the administration of study drug(s)/study procedure
- Whether an alternative etiology has been identified
- Mechanism of action of the study drugs
- Biological plausibility

An AE should be considered ‘related’ to study drug if any of the following are met:

- There is clear evidence to suggest a causal relationship and other possible contributing factors can be ruled out.
- There is evidence to suggest a causal relationship and the influence of other factors is unlikely.
- There is some evidence to suggest a causal relationship (e.g., the AE occurred within a reasonable time after administration of the study drug). However, the influence of other factors may have contributed to the AE (e.g., the patient’s clinical condition or other concomitant AEs).

An AE should be considered ‘unrelated’ to study drug if any of the following are met:

- An unreasonable temporal relationship between administration of the study drug and the onset of the AE (e.g., the AE occurred either before or too long after administration of the product for it to be considered product-related)
- A causal relationship between the study drug and the AE is biologically implausible (e.g., death as a passenger in an automobile accident)
- A clearly more likely alternative explanation for the AE is present (e.g., typical adverse reaction to a concomitant drug and/or typical disease-related AE)

10.1.1.3. Follow-Up of Adverse Events

After the initial AE or SAE report, the investigator is required to proactively follow each patient and provide further information to the sponsor on the patient's condition.

All AEs and SAEs documented at a previous visit/contact and designated as ongoing will be reviewed at subsequent visits/contacts.

All AEs and SAEs will be followed until resolution, the condition stabilizes or is considered chronic, the AE or SAE is otherwise explained, the patient is lost to follow-up or the patient withdraws consent. Once resolved, the appropriate AE or SAE eCRF page(s) will be updated. The investigator will ensure that follow-up includes any supplemental investigations as may be indicated to elucidate the nature and/or causality of the AE or SAE. This may include additional laboratory tests or investigations, histopathological examinations, or consultation with other health care professionals.

The sponsor may request that the investigator perform or arrange for the conduct of supplemental measurements and/or evaluations to elucidate as fully as possible the nature and/or causality of the AE or SAE. The investigator is obligated to assist. If a patient dies during participation in the study or during a recognized follow-up period, the sponsor will be provided with a copy of any post-mortem findings, including histopathology.

New or updated information will be recorded on the originally completed SAE report/eCRF, with all changes signed and dated by the investigator. The updated SAE report/eCRF should be re-sent to the sponsor within the time frames outlined in Section 10.5.1.

10.1.1.4. Laboratory Test Abnormalities

Abnormal laboratory findings (e.g., clinical chemistry, CBC, coagulation, or urinalysis) or other abnormal assessments (e.g., ECGs, X-rays, or vital signs) that are judged by the investigator as clinically significant will be recorded as AEs or SAEs if they meet the definition of an AE (as defined in Section 10.1.1) or an SAE (as defined in Section 10.2).

Clinically significant abnormal laboratory findings or other abnormal assessments that are detected during the study or are present at baseline and significantly worsen following the start of the study will be reported as AEs or SAEs. However, clinically significant abnormal laboratory findings or other abnormal assessments that are associated with the disease being studied, unless judged by the investigator as more severe than expected for the subject's condition, or that are present or detected at the start of the study and do not worsen, will not be

reported as AEs or SAEs. They should only be reported as AEs or SAEs if they induce clinical signs or symptoms, need active intervention, require dose interruption or discontinuation or are clinically significant in the opinion of the investigator.

The investigator will exercise his/her medical and scientific judgment in deciding whether an abnormal laboratory finding or other abnormal assessment is clinically significant.

10.2. Definition of a Serious Adverse Event

An SAE is any untoward medical occurrence that, at any dose:

- Results in death
- Is life-threatening

Note: The term “life-threatening” in the definition of “serious” refers to an AE in which the patient was at risk of death at the time of the AE. It does not refer to an AE which hypothetically might have caused death if it were more severe.

- Requires hospitalization or prolongation of existing hospitalization

Note: In general, hospitalization signifies that the patient was admitted (usually involving at least an overnight stay) to the hospital or emergency ward for observation and/or treatment that would not have been appropriate in the physician’s office or outpatient setting. Complications that occur during hospitalization are AEs. If a complication prolongs hospitalization or fulfills any other serious criteria, the AE is serious. When in doubt as to whether “hospitalization” occurred or was necessary, the AE should be considered serious.

- Hospitalization for elective treatment of a pre-existing condition that did not worsen from baseline is not considered an SAE.
- Hospitalization for social/convenience considerations is not considered an SAE.
- Scheduled therapy for the target disease of the study, including admissions for transfusion support or convenience, is not considered an SAE.

- Results in disability/incapacity

Note: The term disability means a substantial disruption of a person’s ability to conduct normal life functions. This definition is not intended to include experiences of relatively minor medical significance, such as uncomplicated headache, nausea, vomiting, diarrhea, influenza, and accidental trauma (e.g., sprained ankle), which may interfere or prevent everyday life functions, but do not constitute a substantial disruption.

- Is a congenital anomaly/birth defect
- Is considered a significant medical AE by the investigator based on medical judgement (e.g., may jeopardize the patient or may require medical/surgical intervention to prevent one of the outcomes listed above).

The following are NOT considered SAEs:

- Hospitalization for elective treatment of a preexisting condition that did not worsen from baseline
- Hospitalization for social/convenience considerations
- Scheduled therapy for the target disease of the study, including admissions for transfusion support or convenience

10.3. Definition of a Suspected Unexpected Serious Adverse Reaction

A suspected unexpected serious adverse reaction is a serious adverse reaction that is both unexpected (i.e., not present in the study drug's reference safety information) and meets the definition of a serious adverse drug reaction, the specificity or severity of which is not consistent with those noted in the Pamiparib Investigator's Brochure. [59]

10.4. Timing, Frequency, and Method of Capturing Adverse Events and Serious Adverse Events

10.4.1. Adverse Event Reporting Period

After informed consent has been signed but prior to the administration of the study drug, only SAEs should be reported.

After initiation of study drug, all AEs and SAEs, regardless of relationship to study drug, will be reported until 30 days after the last study treatment or initiation of new anticancer therapy.

After a patient is discontinued from the study, investigators are not obligated to actively seek AEs or SAEs from the former patients. After this period, the investigator should report any SAEs that are believed to be related to prior study drug treatment.

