In a recent double-blind Phase 3 study (NOVA), 553 patients with platinum-sensitive, recurrent ovarian cancer were randomized 2:1 to receive a PARP inhibitor niraparib or placebo. [19] Patients were stratified according to presence or absence of a germline *BRCA* mutation (*gBRCA*). The non-*gBRCA* cohort was further classified by HRD status and also included patients with somatic *BRCA* mutations. Patients treated with niraparib had an increased PFS in all cohorts compared with placebo. In the *gBRCA* group, PFS was 21.0 versus 5.5 months (HR 0.27; 95% CI; 0.17-0.41). In the overall non-*gBRCA* cohort, PFS was 9.3 versus 3.9 months (HR 0.45; 95% CI; 0.34-0.61). In the HRD positive (HRD+) subgroup of the non-*gBRCA* cohort, PFS was 12.9 versus 3.8 months (HR 0.38; 95% CI 0.24-0.59). The most common grade 3 or 4 toxicities

associated with niraparib were thrombocytopenia (34%), anemia (25%), and neutropenia (20%). Myelodysplastic syndrome (MDS) occurred in 5 of 367 patients (1.4%) who received niraparib.

Another PARP inhibitor, veliparib, was evaluated in a Phase 2 study in 50 women with a known *BRCA* mutation. Veliparib treatment resulted in a 26% ORR and the median PFS and OS were 8 and 20 months, respectively. [21]

Prostate Cancer

Prostate cancer is the second most common cancer in men worldwide. [22] Recent sequencing data indicates that more than 20% of metastatic castration-resistant prostate cancer (mCRPC) have HRD due to germline and/or somatic loss-of-function in key homologous recombinant genes including *BRCA2*, *ATM*, *CHEK2*, *NSBPI*, *FANCI*, that could potentially confer a ‘BRCAness’ phenotype and susceptibility to PARP inhibition via synthetic lethality. [23, 24, 25, 26] Recently, it has been shown that prostate cancer patients with germline *BRCA1/2* mutations have a higher risk of nodal or distant metastases and poorer overall survival than patients without mutations. [27] Data from clinical studies has demonstrated that these patients respond to treatment with PARP inhibitors. [28]

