1.7. Risk-Benefit Assessment

Pamiparib has been studied in nonclinical toxicity and Phase 1 clinical studies. Pamiparib toxicities are largely consistent with the safety profile shared by other PARP inhibitors with the important exception that pamiparib may cause less myelosuppression. PARP inhibitors, including pamiparib, show a partial overlap with the safety profile of TMZ. Therefore, patients of this study may experience AEs typical for these study drugs at a higher frequency and/or severity. In addition, patients may encounter AEs that are uniquely caused by the novel combination(s). However, with the lower doses of TMZ being used in this study, it is possible there could be fewer myelosuppressive-related AEs than previously seen in other studies using TMZ in combination with PARP inhibitors.

Myelodysplastic syndrome and acute myeloid leukemia (AML) have been reported in a small number (< 1%) of patients treated with PARP inhibitors, especially in patients harboring a germline *BRC A* mutation. [63] Typically, patients who develop MDS and AML while on PARPi therapy had a history of extensive previous chemotherapy and some had a history of previous cancer or bone marrow abnormalities. To date, there have been no reports of MDS or AML in patients treated with pamiparib and no fatal drug reactions. Patients in this study will be monitored monthly for hematological toxicities and events of MDS and AML will be reported as serious AEs (SAEs).

Preliminary data show that pamiparib appears to be generally well tolerated in patients with advanced solid tumors. The safety profile for single-agent pamiparib is similar to that of other PARP inhibitors. Given the dire prognosis of the patients that will be enrolled in this study and

the limited treatment options, the risk of combining pamiparib with TMZ appears acceptable in the context of a Phase 1 study with close monitoring through AE reporting, recording of vital signs and ECGs, clinical laboratory testing, and tumor assessments. As outlined in Section 1.1 and Section 1.6, scientific rationale and supportive data are strong for combining PARP inhibitors with TMZ in TNBC, ovarian cancer, mCRPC, and other solid tumors with homologous recombination deficiency as well as in SCLC and gastric cancer.

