8.5.3. Survival Follow-Up

Patients enrolled during the dose expansion phase of the study will be followed for survival and further anticancer therapy information post progression via phone contact (with the patient's guardian, if applicable) or other means (e.g., clinic visit or review of medical records) approximately every 3 months ([Appendix 1 Table 1](#)).

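### Late MDS/AML is captured only passively: protocol section 1.7 promises SAE reporting without a causality condition, but section 10.4.1 restricts late reports to SAEs believed related, and the 3-monthly contact does not ask

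*Protocol*

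**What the plan says.** **The commitment.** Protocol section 1.7 identifies MDS and AML as risks seen with PARP inhibitors, provides for monthly haematological monitoring, and states that "events of MDS and AML will be reported as serious AEs (SAEs"). It attaches neither a causality condition nor a time limit.

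**The reporting window.** Under section 10.4.1, once study drug has started, all AEs and SAEs of whatever cause "will be reported until 30 days after the last study treatment or initiation of new anticancer therapy". The synopsis makes clear that the earlier limit applies. Section 10.4.1 continues: "After a patient is discontinued from the study, investigators are not obligated to actively seek AEs or SAEs from the former patients". It then adds: "After this period, the investigator should report any SAEs that are believed to be related to prior study drug treatment". No end date is given for that last duty.

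**Contacts after treatment.** In Appendix 1 Table 1, haematology is last scheduled at the EOT visit and AE collection at the safety follow-up. At the safety follow-up, section 8.5.1 requires laboratory tests only for an ongoing abnormality considered related. Section 8.5.3 says that expansion-phase patients "will be followed for survival and further anticancer therapy information post progression via phone contact" or other means, about every 3 months. Footnote 5 of Appendix 1 Table 1 applies the 3-monthly call to all patients and mentions survival status only. Neither text includes MDS, AML or new malignancy.

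**The SAP.** Sections 6.2.1 and 6.4.3 confine AE summary tables to TEAEs. Related SAEs after the treatment-emergent period count as TEAEs, and a missing causality assessment counts as related. All AEs appear in listings. AEs of interest are to be defined before database lock if needed; MDS/AML is not named.

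**The concern.** The unconditional statement in section 1.7 and the conditional rule in section 10.4.1 do not match for events after the 30-day window. For a patient who progresses and moves to another therapy, the window can close before day 30.

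A late case then has to pass two filters: the site must learn of it unprompted, and the investigator must judge it related. Section 10.1.1.2 lets an event be called unrelated when another explanation is clearly more likely. Chemotherapy given after the study could supply that explanation, and section 1.7 itself links these cases to extensive earlier chemotherapy.

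Safety is a primary objective, and the regimen combines a PARP inhibitor with an alkylating agent. Few events are expected, so one or two unrecorded cases could turn an observed signal into a report of none. The protocol does set an event-specific window elsewhere: under section 10.7, pregnancy is reportable up to 6 months after the last dose. MDS/AML has no such provision.

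**Working it through.** **Step 1: which late cases have a route into the data**

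| Case arising after the window | Reporting duty | SAP summary tables |
|---|---|---|
| Site learns of it, judged related | Yes (10.4.1) | Yes, counted as a TEAE (6.2.1, 6.4.3) |
| Site learns of it, judged unrelated | Promised by 1.7, not required by 10.4.1 | No |
| Leads to a death not solely due to progression | Yes, related or not (10.5.4) | Only if related or causality is missing |
| Site does not learn of it | None operates | No |

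The second row is the direct inconsistency. The fourth follows from the absence of any question at the survival contact.

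**Step 2: reproduce the only MDS count in the documents**

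Section 1.2 says: "Myelodysplastic syndrome (MDS) occurred in 5 of 367 patients (1.4%) who received niraparib". 5/367 = 0.01362, or 1.36%, which rounds to the stated 1.4%. The exact 95% confidence interval is 0.44% to 3.15%.

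**Step 3: illustrative total yield**

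Inputs: N = 250 (synopsis, section 4.1). The rate p for this combination is not given. Assumed range: 0.5%, 1.0% and 1.36%. The top value is the single-trial figure above; the lowest lies within the class figure in section 1.7.

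Expected cases = N × p; P(at least one) = 1 − (1 − p)^N.

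- p = 0.5%: 250 × 0.005 = 1.25; P = 71%
- p = 1.0%: 250 × 0.01 = 2.5; P = 92%
- p = 1.36%: 250 × 0.01362 = 3.4; P = 97%

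These are all cases, including those arising on treatment, which the plan does collect. They do not measure the gap.

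**Step 4: late cases**

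The share s arising after the window is not in the documents. Assumed range: 25% to 75%. Expected late cases = N × p × s.

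| p | s = 25% | s = 50% | s = 75% |
|---|---|---|---|
| 0.5% | 0.31 | 0.62 | 0.94 |
| 1.0% | 0.62 | 1.25 | 1.88 |
| 1.36% | 0.85 | 1.70 | 2.55 |

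The range is about 0.3 to 2.6. P(at least one late case) runs from 27% (lowest p and s) to 92% (highest). These cases depend on passive reporting; they are not a count of cases lost. The fraction that would go unreported cannot be calculated.

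**Step 5: what a zero count would appear to show**

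With zero cases in 250, the one-sided 95% upper limit is 1 − 0.05^(1/250) = 1.2%. That limit assumes complete ascertainment over the period described. Without it, the bound cannot be applied to late disease.

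**The case against.** The strongest reply is that the plan has several routes by which a late case can surface.

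- Section 10.4.1 keeps an open-ended duty to report related SAEs, and the SAP counts these as TEAEs.
- The causality threshold in section 10.1.1.2 is a reasonable possibility, and an event can be related even when other factors contributed.
- Blood counts not recovered after 4 weeks prompt consideration of marrow and cytogenetic investigation (section 6.1.3.2). Related events already detected are followed until they resolve or stabilise (section 7.4), so a related cytopenia present at treatment stop does not simply drop out on day 30.
- Deaths not solely due to progression are SAEs regardless of relatedness (section 10.5.4).
- The survival contact records further anticancer therapy and may use medical records, so treatment for AML could come to light there.

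All of this stands. A reader might infer that late cases are simply missed; the documents do not support that. Nor does the sentence about not actively seeking events govern survival follow-up: section 8.6 defines the end of study participation by events such as withdrawn consent, loss to follow-up or death, and patients in survival follow-up have not reached it.

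A reader might also conclude that section 1.7 is wrong to say that MDS and AML "have been reported in a small number (< 1%) of patients treated with PARP inhibitors". That does not follow. It is a class-level statement with its own citation, the 1.4% comes from one trial in recurrent ovarian cancer, and that trial's interval includes values below 1%.

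What the reply does not remove is the dependence on unprompted discovery and a relatedness judgement. No section provides for active enquiry, and a late non-fatal case judged unrelated has no clear route.

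**Conclusion.** The point holds as one of passive capture and possible under-ascertainment. Sections 1.7 and 10.4.1 need to be reconciled for events after the window, and the existing 3-monthly contact lacks the one item that would close most of the gap.

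On the stated assumptions (250 patients, rate 0.5% to 1.36%, 25% to 75% late), about 0.3 to 2.6 late cases would depend on passive reporting. The rate range borrows from other PARP inhibitors and other populations, and the late share is assumed outright. It would be tempting to take the 3.4 cases and 97% as the size of the gap, but those cover all cases and cannot be used that way.

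A reader might also suppose that the choice of RP2D is compromised. The documents do not support that: DLTs are assessed in a 28-day window, and Appendix 1 already states an RP2D for expansion. What is affected is the later description of the combination's safety. This is a worthwhile, inexpensive improvement rather than a flaw that invalidates the safety analysis.

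**What to change.** 1. **Protocol 8.5.3 and Appendix 1:** add one question to each survival contact, asking whether MDS, AML or another new malignancy has been diagnosed since the last contact. Record the answer regardless of causality or later therapy.
2. **Protocol 10.4.1:** state that MDS and AML are reportable at any time, regardless of causality. This brings the section into line with 1.7.
3. **SAP 6.4.3:** add a table of MDS/AML over the whole of follow-up, separate from the TEAE tables, showing the causality assessment and any intervening anticancer therapy.
4. **Protocol 8.5.3 and footnote 5 of Appendix 1 Table 1:** decide whether survival follow-up covers expansion patients only or all patients, and align the two texts. The choice fixes the denominator for the new table: about 200 or about 250.

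The cost is one eCRF item at a contact already scheduled, a short amendment and one table. No extra visit, procedure or treatment rule is involved. The downside is that some cases attributable to later therapy will be recorded; showing the intervening therapy lets readers judge them.
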